Study Protocol and Statistical Analysis Plan

Brief Title: Feasibility of a web-based program to help parents of middle school students effectively communicate with their children about substance use

Protocol ID: Middle Years Study R21-23-003-001

ClinicalTrials.gov ID: NCT05900115

Principal Investigator: [name] ([contact])

IRB Reviewed Protocol Approval Date: 5/1/2023

Study Protocol and Statistical Analysis Plan

The purpose of the project, is to evaluate and assess a self-administered, web-based program, Media Ready Parent (MRP), designed to increase parent knowledge about adolescent substance use, active media mediation skills, and practice high-quality parent-adolescent communication methods. The program will help parents of middle-school aged students, 6th-8th graders, communicate effectively about substance use and enhance media literacy skills to counter unhealthy media messages. Prevention efforts are most impacting for adolescents in middle school years as this is the time frame for growing independence, desire to fit-in and an increase risk for their own experimentation with substances.

The procedure that will be used for conducting the research study is as follows:

1. We will aim for 286 parent-child pairs (child in 6th, 7th, or 8th) to participate in this study. We will aim to have the sample consist of at least 40% fathers or male guardians and no more than 60% white non-Hispanic adult participants. Parent-child pairs will be stratified by parent's gender and race/ethnicity prior to randomization to ensure diversity across groups.
2. A recruitment website will be available. Interested parents can complete an online screener found on the website. If eligible, parents will be directed to a place where parents and their children can complete the online informed consent process. The study team will enroll eligible, consented pairs based on whether there is room in the study according to gender and race/ethnicity stratification. If there is space in the study, parent-child pairs will be randomly assigned to either condition 1) Media Ready Parent (intervention) or 2) active control (i.e., medically-accurate information from sources like the CDC about adolescent substance use).
3. Pretest questionnaires for parents and their children will be distributed to enrolled parents in two separate emails/texts containing a link to complete their respective questionnaires. Participants will have one week to complete their questionnaires. If both the parent and child complete their questionnaire, they will be eligible for a \$30 gift card.
4. Parents will receive a reminder (email, phone call, or text) to complete the pretest questionnaires if both are not completed in the first two business days. If both questionnaires are not completed, the parent will receive a final reminder around the 6th day. See Appendix E for automated messages.
5. Once pretests questionnaires are completed, parents will receive a link to access their randomly assigned resource. The resources could take up to 2 hours to review. Parents will be asked to completely review their assigned resource within two weeks. If they do so, they will be eligible for a \$25 gift card. However, parents will have access to their assigned resource for four weeks (until the posttest questionnaire). Parents will receive a reminder after one week of receiving access to their resources to complete their review within the following week. Parents will receive a final reminder on about the 13th day to complete their review of the resource.
6. About four weeks after pretest questionnaire completion, parents will receive two emails/texts – one with a link to their posttest questionnaire and one with a link to their child's posttest questionnaire. Participants will have one week to complete their

questionnaires. If both the parent and child complete their questionnaire, they will be eligible for a \$50 gift card.

7. Control participants will receive access to MRP after study is completed to review as desired.
8. Incentives will take the form of gift cards. Participants will be able to choose between Amazon and Walmart gift cards. We will mail incentives to participants' physical address after pretest completion (max \$30) and after posttest completion (max \$75).

Statistical Analysis Plan

Preliminary Analyses. Psychometric analyses will be conducted to confirm the reliability, validity, and distributions of key variables. To establish if there is baseline equivalence between groups, we will test for equivalence on basic demographic characteristics (i.e., age, race/ethnicity, gender, and sexual orientation) and on baseline levels of our primary outcome variables in a series of t-test and χ^2 analyses. If we establish that the intervention and control groups are not equivalent on any pre-specified variables, these variables will be used as covariates in the analyses of intervention effects. Missing data will be handled using multiple imputation methods.

Main Analyses. To examine intervention effects on primary outcomes at posttest, we will use a series of linear and logistic regressions in intent-to-treat analyses. For outcomes that have only one informant, posttest scores will be regressed onto pretest scores, covariates, and the treatment effect. Covariates will include parent gender, youth gender, youth age, parent substance use, SES, and supportive parenting.

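### Pairs appear to be randomised at enrolment, before the pretest that releases the resource and dates the posttest; assigning after the pretest would avoid this loss

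*Combined protocol and SAP*

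**What the plan says.** The order comes from the numbered procedure steps in the combined protocol and SAP:

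- Step 1 sets the target: "We will aim for 286 parent-child pairs".
- Step 2 covers enrolment, "The study team will enroll eligible, consented pairs based on whether there is room in the study", and then assignment: "If there is space in the study, parent-child pairs will be randomly assigned to either condition". Space within the gender and race/ethnicity quotas is the only condition given; the pretest is not mentioned.
- Step 3 comes next: "Pretest questionnaires for parents and their children will be distributed to enrolled parents". The window is one week.
- Step 4 foresees non-completion and provides reminders. It does not say what happens to a pair that never completes.
- Step 5 sets the gate: "Once pretests questionnaires are completed, parents will receive a link to access their randomly assigned resource".
- Step 6 sets the outcome date: "About four weeks after pretest questionnaire completion, parents will receive two emails/texts".

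In the SAP, Preliminary Analyses compares the arms "on baseline levels of our primary outcome variables in a series of t-test" and chi-squared tests, and names multiple imputation for missing data without giving a model. Main Analyses specifies intent-to-treat regressions. For outcomes with one informant, the posttest score is regressed on the pretest score, covariates and treatment.

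**The concern.** Randomisation should come as late as practicable, so that few pairs can drop out between assignment and the start of the intervention. Here a full questionnaire round, completed by two people, appears to lie in that gap.

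A pair lost in the gap receives neither resource, and its posttest has no date. Under the ordinary meaning of intent-to-treat it still belongs to the analysis. The imputation would have to supply both its outcome and the pretest score meant to predict that outcome, using screener data and at most one completed questionnaire. If the imputation draws on completers in the same arm, pairs that never saw a resource are given the outcomes of pairs that did. That is not what an intent-to-treat estimate is meant to describe. The planned baseline comparison of outcome levels also has no observed values for pairs that returned neither questionnaire.

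The loss is avoidable, because step 5 already makes the resource wait for the pretest.

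**Working it through.** **Order of the steps.** No sentence dates the randomisation, so the order is inferred. Step 2 makes the assignment conditional on space alone, step 3 addresses parents who are already enrolled, and step 5 speaks of the assignment as existing when the link is sent. Nothing places assignment after the pretest.

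**Inputs.** From the documents: 286 pairs (step 1). Assumed, because the documents give no values: pretest non-completion p of 5%, 10% or 20%; equal allocation (143 per arm); two-sided 5% level; an unadjusted comparison of means with SD 1. The figure of 286 cannot be reproduced, since it comes without power, effect size, SD or dropout allowance. An effect that 286 pairs detect with 80% power is therefore used as a yardstick:

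d = (1.960 + 0.842) × √(4/286) = 0.331 SD.

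**Formulas.**
- Pairs lost = 286p; pairs left = 286(1 − p).
- Power if only the remaining pairs inform the result = Φ(d × √(286(1 − p)/4) − 1.960).
- Power if all 286 are analysed and the lost pairs carry no effect = Φ(d(1 − p) × √(286/4) − 1.960).

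| Assumed p | Lost | Left | Power, remaining pairs | Power, all 286, lost pairs without effect |
|---|---|---|---|---|
| 5% | 14 | 272 | 78.0% | 75.9% |
| 10% | 29 | 257 | 75.7% | 71.3% |
| 20% | 57 | 229 | 70.7% | 61.1% |

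The fourth column is lost precision, and the last is dilution. Which one applies depends on an imputation model and an intent-to-treat set that the SAP does not define.

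**After the change.** With assignment at the step 5 gate, the number of randomised pairs lost at the pretest stage is zero by construction. If 286 pairs consent, 272, 257 or 229 are randomised and the fourth column applies. The number of pairs with outcomes is the same as before.

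**If loss were related to arm (hypothetical).** Suppose 5% of one arm and 15% of the other are lost, and lost pairs differ from completers by g = 0.3 to 0.5 SD in outcome. The completers' contrast then shifts by g × (0.15 − 0.05) = 0.03 to 0.05 SD. About 136 and 122 completers remain (143 × 0.95 and 143 × 0.85), so the standard error is √(1/136 + 1/122) = 0.125 SD. The shift is 0.24 to 0.40 standard errors, and the two-sided type I error rises from 5% to about 5.7% to 6.9%. None of these inputs comes from the documents.

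**The case against.** The best defence is that no harm is shown. The only documented point at which a family meets its arm is step 5, after the pretest. If nobody knows the arm before then, non-completion should be largely unrelated to it. Nor does the change produce any more outcomes: a pair that ignores the pretest gives no posttest under either order, and the randomised sample simply becomes smaller. Concealing the arm until the pretest is done would close the only route to bias without moving anything, and this is a feasibility study.

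Most of that stands. A reader might infer from the order of steps that the comparison is biased. The documents do not support this. Bias would need families or reminder staff to know the arm early and that knowledge to affect pretest completion or answers. Step 4 allows phone calls as well as emails and texts, and refers to automated messages in an appendix outside the supplied text. The text neither shows nor excludes early knowledge of the arm. A reader might also infer that imputation could not correct such bias. That is not established either, because the imputation model and the predictive value of the screener data are unknown.

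A reader might infer that later assignment always gains power. It does so only relative to an analysis that counts lost pairs as carrying no effect; relative to an analysis of the remaining pairs there is no gain. Nor does it clearly improve the stratification, which already covers all randomised pairs if intent-to-treat keeps them.

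The defence does not remove the main point. Concealment makes the loss harmless to the comparison, but still leaves unexposed and mostly imputed pairs in the intent-to-treat set.

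**Conclusion.** The point holds as an avoidable design weakness, not as a demonstrated bias. Followed as written, the plan can leave about 14, 29 or 57 of 286 randomised pairs (at an assumed 5%, 10% or 20% pretest non-completion) with no exposure, no scheduled posttest and little or no pretest data.

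Against a yardstick of 80% at 286 pairs, and at 10% loss, power is 75.7% if these pairs add nothing and 71.3% if they are analysed as carrying no effect. Only the difference between these two figures is affected by the order of steps; the rest follows from families not responding.

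The conclusion rests on the natural reading of steps 2 to 6, on intent-to-treat in its usual sense, and on assumed non-completion rates. Confidence is medium, because the time of assignment is inferred. If the sponsor already assigns after the pretest, one sentence saying so settles the matter.

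**What to change.** Keep the eligibility, consent and quota check at enrolment. Generate the assignment, with the same stratification by parent gender and race/ethnicity, only once step 5's pretest condition is met and immediately before the resource link is sent. Define the intent-to-treat set as all pairs so randomised. Every randomised pair then has the baseline data that the regression and the baseline comparison need. Attrition between pretest and posttest is not affected and still needs the planned imputation.

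The cost is small. Automated steps are re-ordered, and quota places held by pairs still in the pretest stage have to be tracked. If 286 is counted at consent, no extra recruitment is needed.

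If 286 is to be counted at randomisation, 286/(1 − p), rounded up, gives 302, 318 or 358 consented pairs, which is 16, 32 or 72 more. About 14, 29 or 57 more pairs then go through the study. At up to $105 each in gift cards ($30 + $75), that is at most $1,470, $3,045 or $5,985.

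If assignment cannot be moved, conceal it from families and from staff sending reminders until the pretests are complete, and state how a randomised pair without a pretest is followed up and counted. This deals with possible bias but not with the unexposed pairs.

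### Does the SAP allow two tests, and so a doubled false-positive rate, for an outcome that both parent and child report?

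*Combined protocol and SAP*

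**What the plan says.** The opening sentence of Main Analyses sets the method for all primary outcomes: "To examine intervention effects on primary outcomes at posttest, we will use a series of linear and logistic regressions in intent-to-treat analyses". The next sentence gives an equation, but only for part of them: "For outcomes that have only one informant, posttest scores will be regressed onto pretest scores, covariates, and the treatment effect". The sentence after that lists the covariates, and the SAP ends there.

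The procedure shows that two reports could exist for a shared construct. At step 3, "Pretest questionnaires for parents and their children will be distributed to enrolled parents". At step 6 parents receive two messages, "one with a link to their posttest questionnaire and one with a link to their child's posttest questionnaire". The unit of randomization is the pair (step 2: "parent-child pairs will be randomly assigned to either condition"), and the resource goes to the parent (step 5: "parents will receive a link to access their randomly assigned resource").

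The document does not list the primary outcomes or their informants. It states no significance level, sidedness, allocation ratio or multiplicity rule. The only design figure is the recruitment target in step 1: "We will aim for 286 parent-child pairs (child in 6th, 7th, or 8th) to participate in this study".

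**The concern.** The phrase about a single informant has a purpose only if some outcomes have more than one. Communication between parent and child is a natural candidate, because the program aims to have parents "practice high-quality parent-adolescent communication methods" and either member of the pair could rate it. For such an outcome the reader finds no equation and no statement of which report counts.

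If the analyst fits one regression per report, each test is valid on its own, because pairs are randomized. The outcome then has two chances to reach significance. Only the parent receives the resource, so the two reports may well respond differently, and a split result would have no agreed reading. It could be presented as an effect, at close to twice the nominal error, or as no effect. An unadjusted claim from either report would overstate the evidence for the program.

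**Working it through.** **Plan's own figure.** The target of 286 pairs cannot be reproduced. The document gives no significance level, power, effect size, standard deviation, dropout rate or allocation ratio. Everything below therefore rests on assumptions: two-sided 5% per test; correlation ρ between the parent-report and child-report test statistics; and, for power, 286/2 = 143 pairs per arm with complete data.

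**Step 1. False-positive rate under three claim rules.** Let Z₁ and Z₂ be the two test statistics, standard bivariate normal under the null.

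- Either report suffices: 1 − P(|Z₁| < 1.960 and |Z₂| < 1.960).
- Both reports are required: 0.05 + 0.05 − (either).
- Holm over the two reports, at least one rejection: the first formula with 2.241 in place of 1.960.

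| ρ | Either | Both | Holm |
|---|---|---|---|
| 0.2 | 0.0964 | 0.1000 − 0.0964 = 0.0036 | 0.0489 |
| 0.3 | 0.0951 | 0.1000 − 0.0951 = 0.0049 | 0.0484 |
| 0.5 | 0.0907 | 0.1000 − 0.0907 = 0.0093 | 0.0465 |
| 0.7 | 0.0835 | 0.1000 − 0.0835 = 0.0165 | 0.0430 |
| 0.9 | 0.0704 | 0.1000 − 0.0704 = 0.0296 | 0.0362 |

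With ρ = 0 the first column is 1 − 0.95² = 0.0975. One named report, or one joint or composite contrast, is a single test at 0.05 whatever ρ is.

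The same two regressions therefore give anything from 0.4% to 9.6% over ρ = 0.2 to 0.9, depending on a claim rule that the plan does not state. The figure of 9% to 10% belongs to the either-report rule, not to the act of fitting two regressions.

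**Step 2. What the text supports.** The equation is restricted to outcomes with one informant. If each report were simply to get its own regression, that restriction would do no work, because the same equation would serve every report. The wording fits at least as well with some different treatment of two-informant outcomes that was left unwritten. A series of regressions is also compatible with one regression per outcome, on a composite or on one chosen report.

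**Step 3. Would one remedy clearly be best?** Assume a parent effect of 0.33 residual SD and ρ = 0.3. The parent noncentrality is 0.33 × √(143/2) = 2.79. With the child effect a fraction f of the parent effect, the child noncentrality is 2.79f and the composite noncentrality is 2.79(1 + f)/√(2 × 1.3). Power at two-sided 5%:

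| f | Parent report alone | Holm, at least one report | Composite |
|---|---|---|---|
| 0 | 80% | 72% | 41% |
| 0.5 | 80% | 74% | 74% |
| 0.75 | 80% | 80% | 86% |
| 1 | 80% | 88% | 93% |

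Parent report alone is best in the first two rows, and the composite is best in the last two. Holm leads in none, although it avoids the worst loss (41%) when only the parent responds.

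**The case for a change.** The strongest case for a change is that the cause of the silence does not matter. Whether the authors meant separate regressions, a composite or a joint model, none is written down, and a few sentences would settle it without new data. Under the step 3 assumptions, exactly one report would be significant in about 77% of trials if the child effect is zero, 57% if it is half the parent effect and 27% if the two are equal. Split results would be common, and an analyst could read them either way.

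Most of this stands as description. The gap is real, the arithmetic is right, and writing the rule down in advance would be tidier. Three things keep it from being a defect that calls for a change.

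- It is conditional on a two-informant primary outcome, which the document implies but does not show.
- The inflated error needs two additions that the plan does not make: a 5% level per report and a rule that either report suffices. To say that a split result could be read either way concedes that the inflation comes from a choice made after seeing the results, not from the stated analysis.
- Any specific rule put in place of the silence would be a preference. Holm, a named report and a combined contrast all hold the error at or below 5% per outcome, and competent statisticians would choose differently according to how far they expect the child's report to move. Holm within an outcome would also leave untouched the multiplicity across the several unnamed primary outcomes.

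**Conclusion.** The concern does not call for a change to the plan. The SAP leaves the two-informant case unwritten, and that is a gap an analyst can fill sensibly by naming one report, using a composite or joint contrast, or showing both estimates with an adjustment. The plan contains no stated rule that produces a wrong result, and its own error rate for such outcomes is undetermined rather than doubled.

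The figure of 7.0% to 9.6%, for correlations from 0.9 down to 0.2, describes one scenario: two tests at an assumed two-sided 5%, with either allowed to carry the claim. It is useful as a caution when the results are read. If a two-informant outcome is reported, the reader should look for both estimates and give little weight to a claim that rests on whichever report was significant. The power comparison further assumes 1:1 allocation, complete data, a parent effect of 0.33 SD and a correlation of 0.3, none of which the document states.

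### Race/ethnicity is used to stratify but is not a fixed covariate; if it is prognostic, a little power is lost

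*Combined protocol and SAP*

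**What the plan says.** Step 1 of the study procedure stratifies pairs by the parent's "gender and race/ethnicity prior to randomization to ensure diversity across groups". The same step sets enrolment targets of "at least 40% fathers or male guardians" and "no more than 60% white non-Hispanic adult participants". Step 2 makes entry depend on these strata: "The study team will enroll eligible, consented pairs based on whether there is room in the study according to gender and race/ethnicity stratification".

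Under Main Analyses, the SAP fits linear and logistic regressions by intention to treat. For single-informant outcomes, posttest is regressed on pretest, covariates and treatment. The covariates are then listed: "Covariates will include parent gender, youth gender, youth age, parent substance use, SES, and supportive parenting". Parent gender is there; race/ethnicity is not.

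Preliminary Analyses offers one other route. The arms are to be compared by "test for equivalence on basic demographic characteristics (i.e., age, race/ethnicity, gender, and sexual orientation") and on baseline outcome levels, and "If we establish that the intervention and control groups are not equivalent on any pre-specified variables, these variables will be used as covariates". On missing data it says only: "Missing data will be handled using multiple imputation methods".

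**The concern.** The design treats two factors alike and the analysis does not, without giving a reason. A factor used to stratify is normally kept in the model, for two reasons. If it predicts outcome, adjusting removes residual variance. If allocation is balanced within strata, a model that omits the factor also reports a standard error larger than the true one, so the test is conservative.

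The baseline test does not fill the gap. It responds to imbalance, which stratified allocation is meant to prevent, and it takes no account of prognostic value. At stake is a slightly higher chance of missing a real intervention effect.

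**Working it through.** The plan gives no alpha, power target, effect size, SD, event rate or allocation ratio, so it has no figure of its own to reproduce.

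**Inputs from the document:** 286 pairs; 40% male parents and 60% white non-Hispanic (the step 1 limits, used as the mix); pretest plus the six listed covariates.

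**Assumed:** two-sided 5% test; 1:1 allocation; race/ethnicity explains R² of 0 to 10% of residual variance after the listed covariates; 80% power with the factor included. In the main simulations the other three race/ethnicity groups are 15, 15 and 10%, race/ethnicity is independent of the other covariates, and 94% of its variance lies between white non-Hispanic and all others.

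**Linear models, formula.** Let s = √(1 − R²). The standardised effect that gives 80% power with adjustment is 1.960 + 0.842 = 2.802.

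- Balanced within strata, factor omitted: reported SE / true SE = 1/s; type I error = 2(1 − Φ(1.96/s)); power = P(|N(2.802s, s²)| > 1.96).
- Simple randomisation, factor omitted: type I error is nominal; power = P(|N(2.802s, 1)| > 1.96).

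Example at R² = 5%: s = 0.9747, 1/s = 1.026, and balanced power = Φ(2.802 − 1.960/0.9747), about 78.5%.

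| Residual R² | SE too large (balanced) | Type I error (balanced) | Power, balanced | Power, simple |
|---|---|---|---|---|
| 0% | 0% | 5.0% | 80.0% | 80.0% |
| 1% | 0.5% | 4.9% | 79.7% | 79.6% |
| 2% | 1.0% | 4.8% | 79.4% | 79.2% |
| 5% | 2.6% | 4.4% | 78.5% | 78.0% |
| 10% | 5.4% | 3.9% | 76.9% | 75.7% |

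**Linear models, simulation.** There were 10,000 trials per scenario, with blocks of 4 within race/ethnicity × parent gender strata, or simple 1:1. The table shows the change in power, in points, from adding three race/ethnicity indicators (paired Monte Carlo error in brackets).

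| Residual R² | Blocked | Simple |
|---|---|---|
| 0% | +0.1 (0.1) | −0.4 (0.2) |
| 1% | +0.3 (0.1) | −0.1 (0.2) |
| 2% | +0.6 (0.1) | +0.4 (0.2) |
| 5% | +1.3 (0.1) | +1.6 (0.3) |
| 10% | +3.4 (0.2) | +3.6 (0.3) |

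A second calculation anchors 80% on the model without the factor when the factor explains nothing. With stratified allocation it gives losses of 0.3, 0.5, 1.4 and 2.7 points at R² of 1, 2, 5 and 10%.

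**Does the baseline test bring the factor in?** It fired in 0.0% of blocked trials and in 4.4–5.1% under simple randomisation, whatever the factor's effect on outcome.

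**Logistic models.** There were 4,000 blocked trials per setting, with true log odds ratios of 0.72, 0.88 and 1.20 at event rates of 50, 20 and 10%. The factor was added under the collapsing rule set out in the fix. The table shows the change in power in points (paired error 0.1–0.3).

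| Event rate | R² 0% | R² 2% | R² 5% | R² 10% |
|---|---|---|---|---|
| 50% | +0.15 | +0.88 | +1.35 | +2.30 |
| 20% | +0.08 | +0.13 | +1.20 | +1.82 |
| 10% | +0.37 | +0.55 | +1.10 | +1.85 |

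The R² = 0 column is slight overfitting, not a gain. A separate run with a two-level factor of odds ratio 3 gave 79.4% power without it and 81.4% with it, and mean treatment log odds ratios of 0.68 and 0.74.

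**Sparse data.** The chance that at least one category has no events is 1 − Π(1 − (1 − qp)²⁸⁶), with q the category share and p the event rate. With four categories it is 40.5% at p = 5%, 8.1% at 10%, 1.6% at 15% and 0.3% at 20%. With two categories (60/40) it is 0.3% at 5% and below 0.01% at 10%. The table shows separation or non-convergence in 2,000 null trials.

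| Model | 5% events | 10% events |
|---|---|---|
| Factor omitted | 1.5% | 0.0% |
| Three indicators, maximum likelihood | 40.7% | 7.7% |
| Collapsing rule | 1.8% | 0.0% |
| Firth, three indicators | 0.0% | 0.0% |

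Type I error at 5% and 10% events was 3.5 and 5.7% with the factor omitted, 3.5 and 6.0% under the rule, and 4.4 and 5.5% with Firth (Monte Carlo error about 0.5).

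**The case against.** The strongest reply is that this barely matters. No reported conclusion becomes wrong, the residual R² is unknown, and pretest and SES, both already in the model, may absorb most of what race/ethnicity would explain. All of that stands.

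Under simple randomisation the formula also overstates what can be recovered, because it ignores the cost of estimating three indicators. The model without them has 286 − 9 = 277 residual degrees of freedom, so they add about 3/277 = 1.1% to the variance. That matches the simulated −0.4 points at R² = 0 and puts break-even near R² = 1%. This stands too. Likewise, netting off the R² = 0 column leaves logistic gains at R² = 2% of about 0.7, 0.05 and 0.2 points at event rates of 50, 20 and 10%; the last two are within simulation error.

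Step 2 can be read as describing enrolment quotas, and no blocking is mentioned. If allocation is not balanced within strata, the point about the reported SE falls away but the power loss remains.

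Finally, the stratification categories are not stated and the 15/15/10% split is assumed. The four-category sparse-data risk depends on that split, and the logistic gains under collapsing depend on most of the variance lying in the contrast that is kept. These points limit the benefit. They do not remove the mismatch, and no other part of the plan fixes race/ethnicity in the model.

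**Conclusion.** The concern holds, and it is small. One stratification factor is fixed in the model, while the other depends on a test that almost never fires when allocation is balanced and that ignores prognosis in any case. By formula, the linear loss is under 1 point of power if race/ethnicity explains 2% or less of residual variance, and about 3 to 4 points at 10%. Any error is on the conservative side. The sizes rest on the assumed R² range, the 80% anchor, 1:1 allocation and the assumed group mix. The change is worth making because it is nearly free and matches analysis to design, not because the present plan would mislead.

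**What to change.** Add parent race/ethnicity, in the categories used to stratify, to the prespecified covariates of the linear and logistic models and to the imputation model, whatever the baseline test shows.

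For binary outcomes, prespecify a sparse-data rule that does not look at treatment arm. For example: if any category has fewer than 5 events or fewer than 5 non-events, counted over both arms together in the observed data, collapse to white non-Hispanic versus all others, the split behind the enrolment limit in step 1. If that is still too sparse, use a penalised (Firth) logistic model. State that the odds ratios are conditional on the covariates.

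The cost is SAP wording and a few degrees of freedom. Step 2 requires the variable before assignment, so nothing new is collected. Collapsing recovers less power if the differences lie among the smaller groups. If the sponsor prefers to leave the factor out, the SAP should say why.
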